Postbaseline measurements are collected after study drug administration through Week 16 (Visit 8) or early discontinuation visit. Efficacy data collected at scheduled visits (e.g., eCOA, ClinRO) will be used in all analyses unless it is missing. If an assessment is missing at a scheduled visit, an unscheduled post-baseline assessment can be used provided it falls within the window interval as follows: a ± 2 day window is used for Visit 3 (Week 1), Visit 4 (Week 2), and Visit 5 (Week 4); and a ± 4 day window is used to Visit 6 (Week 8), Visit 7 (Week 12), and Visit 8 (Week 16). If there is more than 1 unscheduled visit within the defined visit window and no scheduled visit assessment is available, the unscheduled visit closest to the scheduled visit date will be used. If two unscheduled visits of equal distance are available, then the latter of the two will be used.

Postbaseline daily diary endpoints will be the mean of weekly visit windows (diary windows) anchored on day of first dose (Day 1) and day of Week 16 scheduled visit. Weeks 1-14 are defined as follows:

Week	Days
1	1-7
2	8-14
3	15-21
4	22-28
5	29-35
6	36-42
7	43-49
8	50-56
9	57-63
10	64-70
11	71-77
12	78-84
13	85-91
14	92-98

The Week 16 diary window is the 7 days prior to the scheduled Week 16 visit. If there is no Week 16 scheduled visit, the 7 days prior to the last visit (whether scheduled or unscheduled)

occurring after Day 105 constitutes the Week 16 diary window if one exists. If there is no visit on which to anchor the Week 16 diary window, the Week 16 interval and its associated mean are defined as missing. If there are less than 4 non-missing assessments in the Week 16 diary window, the interval can be extended up to 7 additional days, one at a time, to obtain the most recent 4 non-missing values. The assessment of whether 4 non-missing values exist in the Week 16 diary window, and subsequent extension of that window, does not consider censored data in window construction (i.e., they are counted as non-missing unless they are truly unobserved). If the Week 16 diary window has less than 4 non-missing values after extending the Week 16 diary window up to a maximum of 14 days, the Week 16 diary window is defined as 7 days and the mean of the window is missing.

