If a patient has more than 1 event of herpes simplex, the event with the maximum severity will be used in these summary tables. If more than 1 event of herpes simplex occurs with the same severity, the event with the longest duration will be used in the summary table.

Skin Infections

A summary analysis of skin infections will be provided. Skin infections will be defined based on MedDRA preferred term as listed in Compound level safety standards.

HBV DNA

A listing of patients with detectable hepatitis B virus (HBV) deoxyribonucleic acid (DNA) post baseline will be provided.

HBV DNA status post baseline (not detectable, detectable but not quantifiable [i.e., LLOD], quantifiable [i.e., LLOD]) will be summarized by treatment group stratified by baseline HBV serology status, specifically:

- HBsAb+ / HBcAb+
- HBsAb- / HBcAb+

Association between infection and neutropenia/lymphopenia

To evaluate the association between infection and neutropenia, for the controlled analysis sets, the frequency of infections will be provided by patient subgroups defined by the worst CTCAE grades of neutropenia during the analysis period, respectively. Infection outcomes considered for this analysis are any treatment-emergent infection, serious infection and herpes zoster. For this analysis, no statistical comparison will be provided.

In addition, and depending on the number of cases with CTCAE Grade 2 or greater, a summary table will be provided for treatment-emergent infections that were preceded or accompanied by neutropenia. For this analysis, neutropenia is defined as (1) CTCAE Grade 2 or greater, (2) Grade 3 or greater. Infection events with onset date ≤ 14 days before or after the Grade 2 neutrophil count collection date will be considered as infections preceded or accompanied by neutropenia.

Similar analyses as above will be conducted to evaluate the association between infection and lymphopenia.

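### The infection–neutropenia table uses two grade thresholds but ties infections to a single Grade 2 count date, so the Grade 3 or greater definition has no anchor of its own

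*SAP*

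**What the plan says.** The last part of SAP section 6.14.5.6 (Infections) plans two analyses of infection and neutropenia.

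- The first gives infection frequency in "patient subgroups defined by the worst CTCAE grades of neutropenia during the analysis period". It uses no dates.
- The second is conditional: "depending on the number of cases with CTCAE Grade 2 or greater, a summary table will be provided". It covers treatment-emergent infections around the time of a low count. For this table "neutropenia is defined as (1) CTCAE Grade 2 or greater, (2) Grade 3 or greater".

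The linking rule for the second analysis follows at once. It selects "Infection events with onset date ≤ 14 days before or after the Grade 2 neutrophil count collection date". Those are the infections that the table treats as linked to a low count. No other anchor date is given, and nothing says that the anchor changes with the definition in use.

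The approach then carries over to lymphocytes: "Similar analyses as above will be conducted to evaluate the association between infection and lymphopenia".

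**The concern.** Two thresholds are in use, and the date rule names one grade. For the rule to serve both definitions, the count that opens the 14-day window would have to be one that satisfies the definition being tabulated. The sentence does not say so.

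Two things can go wrong. An infection at a count worse than Grade 2 may have no anchor date at all. An infection close to a Grade 2 count may be carried into the tabulation for the more severe definition because the patient reached Grade 3 at some other time. The second definition exists to isolate the lowest counts, which is where a link with infection is of most safety interest. Two programmers could also follow the sentence in good faith and produce different tables.

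The point is which count serves as the anchor. It is not about the window running both before and after the count.

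**Working it through.** The SAP gives no figure to reproduce here. The check is to apply the rule to example patients under the two possible readings. All patient dates below are assumed for illustration.

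**Inputs (SAP section 6.14.5.6).** Definition 1: Grade 2 or greater. Definition 2: Grade 3 or greater. Window: |onset date − anchor date| ≤ 14 days. Anchor: the Grade 2 count.

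**Readings.** Literal: the anchor is a count of exactly Grade 2. Lenient: the anchor is any count of Grade 2 or greater.

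**Case A.** The only abnormal count is Grade 3, on Day 57. Infection starts on Day 60, so the gap is 60 − 57 = 3 days.
- Literal: there is no Grade 2 date, so the infection is linked under neither definition.
- Lenient: the Day 57 count is an anchor, so the infection is linked.
- With an anchor matched to each definition: linked under 1 and 2.

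**Case B.** Grade 2 count on Day 29, infection on Day 33, Grade 3 count on Day 85. The gaps are 33 − 29 = 4 days to the Grade 2 count and 85 − 33 = 52 days to the Grade 3 count.
- Literal and lenient: the infection is linked through the Day 29 count. The patient also meets definition 2, and the linking sentence does not keep the infection out of that tabulation.
- With an anchor matched to each definition: linked under 1 only.

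Case A fails on the literal reading only. Case B is left open on both.

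**A hypothetical extreme for the literal reading.** Assume that counts are taken only at scheduled visits. SAP section 6.2.2 lists Week 4 and then "Visit 6 (Week 8), Visit 7 (Week 12), and Visit 8 (Week 16"), which are 4 × 7 = 28 days apart. Those visits are listed there for efficacy windows, so using them for blood counts is an assumption. Assume also a Grade 3 count at Week 8, Grade 2 counts at Weeks 4 and 12, and no repeat counts.

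Let *d* be the infection onset relative to the Week 8 count, from −14 to +14. That is 14 + 1 + 14 = 29 possible days.
- Distance to the Week 4 count is 28 + *d*, which is ≤ 14 only if *d* ≤ −14, so only at *d* = −14.
- Distance to the Week 12 count is 28 − *d*, which is ≤ 14 only if *d* ≥ 14, so only at *d* = +14.

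The literal rule therefore captures 2 of 29 days. With no Grade 2 count at all it captures 0 of 29. On the lenient reading the Week 8 count is itself an anchor and all 29 days are captured.

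**The case against.** The strongest reply is that this is shorthand. The same paragraph refers to Grade 2 or greater twice just before, once as the condition for making the table and once as definition 1. A reader could take the Grade 2 count to mean that threshold, and then nothing is lost under definition 1. This is a fair reading, and it removes the Case A problem. It is not secure: the paragraph writes the words for *or greater* each time it states a threshold and omits them only here, and section 6.14.5.2 likewise writes *or above* when it means a range. Nor does it give definition 2 an anchor.

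A second reply is that definition 2 itself should keep Case B out, because an infection near only a Grade 2 count is not accompanied by neutropenia as that definition has it. That is the sensible intention. The SAP does not direct the misplacement; it leaves it possible, because the only sentence that says which infections count uses the Grade 2 date without distinguishing the definitions.

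Third, the safety question is partly covered elsewhere. The worst-grade analysis uses no dates, and section 6.14.5.6 also provides for review of infections with laboratory data in a listing. Both points stand. The compound level safety standards might state the anchor, but they are not available here and this paragraph does not cite them for the rule.

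Finally, the 2-of-29 figure is contrived. It needs the literal reading, a particular sequence of grades and no repeat counts, while section 6.14.5.2 includes unplanned measurements in the haematology abnormality analyses. This stands in full.

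**Conclusion.** The linking sentence does not implement the second of its two definitions and should be corrected. That conclusion holds on either reading of Grade 2. The outright loss of infections at Grade 3 or 4 counts is narrower: it requires the literal reading and no Grade 2 count within 14 days of onset.

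A reader might infer more, and the SAP does not support it:
- That infections at the lowest counts are simply missed, or that some 27 of 29 days are lost. The SAP gives no haematology schedule, and closer or repeat counts would reduce any loss. The figure shows how the rule behaves at a hypothetical extreme and is no estimate of impact.
- That a Grade 3 row will be filled from Grade 2 dates. No table layout is shown, and the text permits this error without requiring it.
- That the trial's safety conclusions are at risk. The table is supportive and produced only if there are enough cases. The worst-grade subgroup analysis and all efficacy results are unaffected.

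This is a minor point, worth making because the correction is easy and removes a real ambiguity.

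**What to change.** In section 6.14.5.6, replace the anchor at the end of the linking phrase with: *the collection date of any neutrophil count meeting the definition being tabulated (Grade 2 or greater for definition 1; Grade 3 or greater for definition 2)*. State that the same wording applies to lymphocyte counts, so that the lymphopenia analysis does not inherit the fault.

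With this wording Case A counts under both definitions and Case B under the first only. Because any qualifying count will do, patients with several low counts are also covered. The cost is one sentence of SAP text and the matching programming specification. No new data are needed, and no clinical rule or other analysis changes.

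### The infection–neutropenia table pools infections that began, and may have ended, before the low count with those that followed it, and dates its Grade 3 row from a Grade 2 count

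*SAP*

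**What the plan says.** Section 6.14.5.6 of the SAP, under the association between infection and neutropenia/lymphopenia, plans two displays.

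- The first gives infection frequency by "patient subgroups defined by the worst CTCAE grades of neutropenia during the analysis period". It is descriptive: "For this analysis, no statistical comparison will be provided".
- The second is conditional, "depending on the number of cases with CTCAE Grade 2 or greater". If it is produced, "a summary table will be provided for treatment-emergent infections that were preceded or accompanied by neutropenia".

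For the second display, "neutropenia is defined as (1) CTCAE Grade 2 or greater, (2) Grade 3 or greater". The linking rule takes infections with an onset date no more than 14 "days before or after the Grade 2 neutrophil count collection date will be considered as infections preceded or accompanied by neutropenia". The rule does not require an infection with earlier onset to be still ongoing when the blood was drawn.

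The section closes with: "Similar analyses as above will be conducted to evaluate the association between infection and lymphopenia".

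**The concern.** The label of the second table carries a time order: the low count came first, or the two were present together. The rule that fills the table carries none, because it treats 14 days before the count and 14 days after it alike. An infection that was over before the first low count satisfies the rule, yet on the recorded data it was neither preceded nor accompanied by neutropenia.

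Direction matters here. An infection may itself lower the count, and it may prompt the blood draw that finds the low value. Section 6.14.5.2 includes unplanned measurements in the graded haematology analyses. If the same data feed this table, a count taken because the patient was ill can become the anchor date, and the backward half of the window then picks up the infection that prompted it.

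The second problem is the anchor. Two grade thresholds are defined, but only a Grade 2 collection date is named. Two programmers could fill the Grade 3 or greater row differently. The grouping by worst grade does not settle either matter, since it has no time order.

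**Working it through.** The SAP gives no event count, rate or power figure for this table, so there is nothing to reproduce. The check is a day count and a comparison of the label with the rule.

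**Window.** Let day 0 be the collection date of the low count.

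- Qualifying onset days as written: 14 before + 1 on the day + 14 after = 29.
- Onset days before the count: 14, and 14/29 = 48%.
- Onset days on or after the count: 1 + 14 = 15, and 15/29 = 52%.

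The 48% would equal the share of tabulated infections only if onsets were spread evenly over the window. The SAP neither supports nor refutes that.

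**Label against rule, by type of infection.**

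| Infection | Admitted by the rule? | Supported by the label? |
|---|---|---|
| Onset on the collection date or up to 14 days after | Yes | Yes |
| Onset 1–14 days before, ongoing at collection | Yes | Yes, as accompanied |
| Onset 1–14 days before, falling between two consecutive low counts | Yes | Reasonably, as accompanied |
| Onset 1–14 days before, resolved before collection, no earlier low count | Yes | No |

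An illustration of the last row: onset on Day 15, resolution before Day 28, first Grade 2 count on Day 28. The gap is 28 − 15 = 13 days, so the infection is tabulated, although no low count is documented before it or during it.

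**Anchor.** Take a patient with a Grade 2 count on Day 28 and a Grade 3 count on Day 84.

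- Literal window from the Grade 2 date: 28 − 14 = Day 14 to 28 + 14 = Day 42.
- Window from the Grade 3 date: 84 − 14 = Day 70 to 84 + 14 = Day 98.

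The two windows do not overlap. On the literal reading, any infection counted in the Grade 3 row began at least 84 − 42 = 42 days before the Grade 3 count, and an infection close to that count is left out. A patient who goes straight to Grade 3 has no Grade 2 date, and so no window at all.

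Because the lymphopenia analyses are to be similar, both features carry over.

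**The case against.** Several stronger readings are tempting, and the document does not support them.

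- A reader might infer that infections which came first are reported as following neutropenia. The label is a joint one, however, and an infection with earlier onset that is still present at the blood draw fits *accompanied*. Counts are known only on collection dates, so the neutrophils may already have been low at onset. Earlier onset does not prove that the infection came first; it means only that the reverse is not documented.
- A reader might infer that about half of the tabulated infections are out of order. The 48% is a share of days and says nothing about infections without an assumption about when onsets fall.
- A reader might infer that the SAP has no other way to look at timing. Section 6.14.5.6 also plans a listing of treatment-emergent infections for review alongside laboratory parameters, and Section 6.14.5 allows patient profiles or listings, where needed, to follow the time course of cases. Further detail is left to a compound-level standards document that is not at hand.

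The defence can add that the stated aim is association, not cause; that the table is conditional and no test is specified for it; and that with sparse blood sampling a two-sided window is a sensitive screen. It can also say that the named Grade 2 date may be shorthand for the qualifying count.

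Most of this stands, and it limits the consequence. It is a good reason to keep the two-sided window and not to discard earlier-onset infections. It does not make the label right for an infection that ended before the count, and it does not state the anchor for Grade 3 or greater.

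**Conclusion.** The point holds in a limited form. The rule admits infections that the label does not cover, namely those that began and resolved before a documented low count, and it merges the two time orders into one row. The date used for the Grade 3 or greater row is wrong or undefined if the text is read literally, and at best unstated.

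The number of infections affected cannot be known from the SAP. What is certain is that 14 of the 29 qualifying onset days precede the count. How many of the infections on those days are mislabelled depends on how many were over by the collection date with no earlier low count.

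The consequence is confined to how this descriptive safety table and its lymphopenia counterpart are read. No efficacy result and no analysis under multiplicity control is touched. It is worth correcting because the correction is cheap and keeps every event visible.

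**What to change.** - Keep the 14-day window, but show two rows: onset on or after the collection date (days 0 to 14), and onset 1–14 days before it.
- In the earlier-onset row, use *accompanied* only where the infection was ongoing at the collection date or fell between two consecutive low counts. Label the remainder as starting within 14 days before the count.
- Anchor each definition on its own qualifying count: a Grade 2 or greater count for the first, a Grade 3 or greater count for the second. State which count applies when a patient has several.
- Apply the same rules to lymphopenia.

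Leave the table by worst grade as it is. It may seem natural to give infected patients their worst grade on or before onset, but uninfected patients would keep the worst grade over the whole period. Infected patients would then have less time to reach a high grade, and the table would be biased against showing an association.

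The cost is SAP wording and minor programming. No new data are needed: the same section already ranks repeated herpes events by duration, and Section 6.14.5.11 lists adverse event onset and end dates, so the required dates are held. The downside is fewer events per row.

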6.14.5.7. Major Adverse Cardiovascular Events (MACE) and Other Cardiovascular Events

Potential major adverse cardiovascular events (MACE) and other cardiovascular events requiring adjudication will be analyzed.

Categories and subcategories analyzed will include, but are not limited to, the following:

- MACE

- Cardiovascular death,
- Myocardial infarction (MI),
- Stroke,
- Other cardiovascular events
 - Transient ischemic attack,
 - Hospitalization for unstable angina,
 - Hospitalization for heart failure,
 - Serious arrhythmia,
 - Resuscitated sudden death,
 - Cardiogenic shock,
 - Coronary interventions (such as coronary artery bypass surgery or percutaneous coronary intervention),
- Non-cardiovascular death,
- All-cause death.

In general, events requiring adjudication are documented by investigative sites using an endpoint reporting CRF. This CRF is then sent to the adjudication center which uses an adjudication reporting CRF to document the final assessment of the event as a MACE, as some other cardiovascular event, or as no event (according to the Clinical Endpoint Committee Charter). In some cases, however, the investigator may not have deemed that an event had met the endpoint criteria but the event was still sent for adjudication as a potential MACE, other cardiovascular event, or no event. These events are included in the adjudication process to ensure adequate sensitivity. In these instances, the adjudication reporting CRF will not have a matching endpoint reporting CRF from the investigator. Events generated from these circumstances will be considered as events sent for adjudication in the absence of an investigator's endpoint reporting form.

The number and percentage of patients with MACE, other cardiovascular events, non-cardiovascular death, and all-cause death, as positively adjudicated, will be summarized by treatment group based on the categories and subcategories above.

A listing of the events sent for adjudication will be provided to include data concerning the MedDRA PT related to the event, the seriousness of the event, and the event outcome, along with the adjudicated result.

6.14.5.8. Venous and Pulmonary Artery Thromboembolic (VTE) Events

Events identified as representative of VTE disease will be classified as Deep Vein Thrombosis (DVT), pulmonary embolism (PE), or other peripheral venous thrombosis and will be analyzed. The following definitions apply:

- DVT: Clinical diagnosis of a thrombosis in a deep vein above the knee that must be confirmed by objective evidence of either: a filling defect of deep veins of the leg on venography or a non-compressible venous segment on ultrasound or confirmation by other imaging modality (e.g., Computed tomography [CT], Magnetic Resonance Imaging [MRI]).

- PE: Clinical diagnosis of pulmonary embolus that must be confirmed by objective evidence of either: a filling defect of pulmonary arteries by either pulmonary angiography or CT angiography or by a high probability Ventilation Perfusion (VQ) scan.
- Other Peripheral Venous Thrombosis: Clinical diagnosis of a venous thrombosis not specified by either DVT or PE above. Other peripheral venous thrombosis disease must be confirmed by objective evidence by imaging including venography, ultrasound, CT scan, or MRI. Examples of these would include thrombi in calf (i.e., below the knee), portal vein, subclavian vein, or mesenteric vein. Superficial thrombophlebitis alone is not considered a VTE event.
- Other peripheral venous thromboses of the lower limbs: DVT (above knee) and non-superficial below knee thromboses will also be summarized.

In general, events requiring adjudication are documented by investigative sites using an endpoint reporting CRF. Refer to Section 6.14.5.7 for more details as the process is the same as that of MACE.

The number and percentage of patients with a VTE according to the 4 classifications defined above, as positively adjudicated, will be summarized by treatment group.

A listing of the VTE events sent for adjudication will be provided to include data concerning the MedDRA PT related to the event, the seriousness of the event, and the event outcome, along with the adjudicated result.

